7.1 Study Design

This is a prospective open label phase IV observational study

Primary Endpoint:

Change in the number / proportion of T2 related cellular populations in BAL including ILC2, Th2, alveolar macrophages, eosinophils and basophils pre- and post benralizumab (12 weeks).

Secondary Endpoints:

1. Change in cellular populations and gene expression of T2-related signalling pathways in bronchial biopsies pre- and post benralizumab
2. Change in type 1 & 3 interferon production and viral replication following infection of cultured BECs and alveolar macrophages with RV-16 and examine the response of cells to SARS-CoV-2 collected pre- and post- benralizumab.
3. Change in cellular populations and gene expression of remodelling-related pathways in bronchial biopsies pre- and post benralizumab
4. Change in airway oscillometry measures and MRI measures of ventilation pre- and post benralizumab.

Each recruited participant will be in the study for 3 months and will attend for 8 visits including screening and informed consent. Visits will include blood, breathing tests and bronchoscopy. Participants will undergo bronchoscopy twice in a 12 week period (pre- and 12 weeks post benralizumab treatment). Processing of biological samples and data from clinical measures will be mined throughout the study period of 24 months and also when patients revert to ongoing NHS clinical care that is standard for those on benralizumab treatment for their asthma.

Gantt Chart: The total study duration is 24 months.

Months	3	6	9	12	15	18	21	24
Ethics application and approval								
Patient recruitment, bronchoscopies and sample collection and laboratory procedures								
BEC and mac culture for anti-viral immunity								
BEC and Br biopsy Spatial transcriptomics								
Protein analysis								
Data analysis								
Manuscript(s) preparation								

Treatment Regimen:

Benralizumab will be commenced according to UK NICE severe asthma guidance with 30mg sc dosing every 4 weeks for first 3 doses, followed by every 8 weeks.

Design and patient flow:

- Visit 1: Consent, Enrollment and schedule of visit dates
- Visit 2: Day 1 Covid-19 test
- Visit 3: Day 2 Bronchoscopy
- Visit 4: Day 10 Subject receives benralizumab dose 1 (30mg subcutaneous injection)
- Visit 5: Day 38 Subject receives benralizumab dose 2 (30mg subcutaneous injection)
- Visit 6: Day 66 Subject receives benralizumab dose 3 (30mg subcutaneous injection)
- Visit 7: Day 83 Covid-19 test

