The PIS will explain that the study involves 2 bronchoscopies and it is hoped that patients do not drop out of the study prior to the second bronchoscopy. We will work with our Patient Research Ambassadors to support retention. If patients decide to drop out they will continue to receive benralizumab as per the plan from the multidisciplinary team (MDT) and patients will be replaced until the desired paired sample numbers are reached. The clinical investigators are experienced in recruiting patients as well as performing bronchoscopies on patients with severe asthma and a standardised sedation and periprocedural protocol will be used to maintain consistency in sampling and patient experience.

Patients can withdraw from the study at any time. This will not affect their care or treatment within Guy's Severe Asthma Service and in particular will not affect ongoing delivery of benralizumab.

Sample Size Justification:

Based on the observed 85% responder rate to benralizumab in our centre (Kavanagh et al. CHEST 2021), statistically significant falls in FeNO observed in FeNO-high patients with benralizumab, and successful published transcriptomics studies in asthma of a similar number, we believe 12 subjects should yield at least 10 clinical responders to benralizumab. Twelve is also an achievable amount from a practical perspective to allow timely completion of this study in under 18 months from first subject in (FSI).

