10.3 Sample Analysis Procedures

The aim is to study the influence of benralizumab on structural and inflammatory airway cells in patients with severe eosinophilic asthma.

Our primary outcome measure is:

The change in the number / proportion and/or activation status of Type-2 related cellular populations in samples derived from bronchoscopy including bronchial biopsies, bronchoalveolar lavage (BAL) and bronchial brushings. These cells include ILC2, Th2, alveolar macrophages, epithelial cells, eosinophils and basophils pre- and post- 12 weeks of benralizumab using molecular techniques.

Secondary Endpoints:

To investigate the following before and after completing treatment with 12 weeks of benralizumab.

1. Changes in epithelial barrier integrity using cell biology methods such as transepithelial resistance or barrier permeability.
2. Changes in epithelial antiviral responses in untreated vs respiratory virus-infected cells including rhinovirus-16 and SARS-CoV-2 using protein and nucleic acid analyses.
3. Changes in the antiviral responses of alveolar macrophages to rhinovirus-16 or other respiratory virus infection using protein and nucleic acid analyses.
4. Changes in epithelial responses to cytokines/chemokines and/or exposure to other cell types (co-cultures).
5. Changes in airway remodelling by histological examination.
6. Changes in the profile and function of isolated structural cells (such as airway smooth muscle and epithelial cells but not restricted to) dissected from larger biopsies by molecular and cellular methods.
7. To evaluate the impact on peripheral airways by obtaining bronchoalveolar lavage (BAL) and performing nucleic acid and protein analyses
8. Peripheral airway dysfunction using tests such as impulse oscillometry but not restricted to.
9. Change in FeNO levels.

Study procedures- Clinical Assessment

The CRF will be completed and include clinical details about asthma and other relevant medical conditions and medications.

Spirometry

Spirometry will be conducted in hospital using a spirometer conforming to ATS/ERS standards as specified by the manufacturer's instructions. FEV1 (L), FVC (L), FEV1/FVC ratio, FEF25-75 (% of predicted value) and PEF (L/min) will be recorded. FEV1, FVC and PEF will be documented as both absolute values and as a percentage of the predicted value.

Oscillometry

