Oscillometry is a non-invasive measure of pulmonary resistance and reactance. By measuring oscillating pressures/flow signals of moving air within the lungs, when generated at different frequencies, it provides measures of airway mechanics from different lung regions. Generally lower frequencies, in particular frequency dependent changes in resistance between 5 and 20 Hz and capacitive reactance at 5 Hz are thought to reflect changes arising in the more distal airways. Oscillometry will be performed pre- and post-bronchodilator.

Fractional nitric oxide (FeNO)

FeNO is a surrogate marker of T2-airway inflammation. FeNO will be measured using a NIOX VERO device, as specified by the manufacturer's instructions. This includes collection by controlled exhalation at the recommended controlled expiratory flow rate of 50ml/s for greater than 6 seconds.

Blood sampling

Blood will be collected for routine full blood count (including blood eosinophil and basophils), biochemistry and coagulation measurements pre-bronchoscopy. In addition plasma/ serum will be stored for proteomic/nucleic acid analyses.

Bronchoscopy

Bronchoscopy will be conducted according to established guidelines, and will be performed by respiratory physicians experienced in bronchoscopy. Participants will receive nebulised salbutamol (2.5mg) and ipratropium bromide (500mcg) prior to the procedure. Local anaesthesia will be achieved with gel applied to the nasal passages and lignocaine spray to the throat, soft palate and pharynx. Intravenous sedation using midazolam (maximum 5 mg) and alfentanil (maximum 500 mcg) will be given to achieve conscious sedation. A flexible bronchoscope will then be passed either through the nose or mouth into the lungs with additional lignocaine spray being applied to prevent coughing.

- i) Bronchial brushings will be performed using single-use brushes. Up to a total of 6 brushes will be taken.

- ii) Bronchial biopsies will be performed from the lower and middle lobes using single use forceps. Up to 6 evaluable biopsies will be taken.
- iii) Bronchoalveolar lavage (BAL): the bronchoscope will be inserted in a sub-segmental bronchi and 60ml aliquots of pre-warmed 0.9% saline will be instilled followed by gentle suction to recover lining fluid. This will be repeated up to 3 times.

At the first bronchoscopy (Visit 3) samples will be collected from the right side of the lung and at second bronchoscopy (Visit 8) samples will be taken from the left side.

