14.2 Statistical analysis

Descriptive statistics will be used for demographic and clinical characteristics of the study subjects. The primary comparisons are pre- and post-benralizumab therapy. Clinical outcome measures (asthma control scores, exacerbation frequency, medication use, lung function obtained at baseline and following benralizumab treatment will be evaluated using standard statistical tests. These statistical tests are either parametric paired t-tests or non-parametric U-tests for continuous variables, and fisher tests for the analysis of proportions. We will also leverage on local statisticians when needed.

Statistical comparisons in RNA-seq will be undertaken using currently available pipelines such as DESeq2. DESeq2 has in-built modelling based on binomial distributions of RNA-seq datasets and is well established and validated. Likewise we will follow the most up to date pipelines for analysis of spatial transcriptomics as per 10xgenomics, which include combining spatial information with single cell RNA-seq-type analyses.

Employing spatial transcriptomics, we will compare the effect of benralizumab on cell-specific gene expression changes, cell numbers and position within bronchial biopsies, as well as cell-to-cell interactions.

Employing RNA-seq on BECs, we will compare (1) unstimulated BECs pre- and post- benralizumab, and (2) SARS-CoV-2/RV-16 infected BECs pre- and post- benralizumab, determining the effect of benralizumab on the antiviral response of BECs to each one of these viruses separately.

All analyses will be paired, considering patient-specific changes.

All analyses involving the measurement and comparison of multiple variables (e.g. RNA-seq) will include a multiple test correction, such as false discovery rate / Bonferroni.

15 Ethical considerations

Study will go through R&D and REC approval.

Patients will give informed consent

16 Financing and Insurance

The study is being funded by Astra Zeneca.

The Chief Investigator is employed by KCL so additional indemnity cover is provided by the College As the study is co-sponsored by GSTFT, clinical negligence is provided via the NHS Indemnity Scheme.

17 Reporting and dissemination

Any pilot data arising from this study, and which is statistically robust will be presented at conferences. At the end of the study period, following data analysis completion, a manuscript will be prepared for peer review and publication.

Tables, Figures, References

Appendices

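### The biopsy rule in section 10.3 names a lobe that the left lung does not have, so it can be followed in full at Visit 3 (right lung) but not at Visit 8 (left lung), and biopsy lobe may differ before and after treatment.

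*Protocol*

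**What the plan says.** The Bronchoscopy part of section 10.3 gives the biopsy location: "Bronchial biopsies will be performed from the lower and middle lobes using single use forceps". It sets no restriction by visit or side. On number it says "Up to 6 evaluable biopsies will be taken", with no split by lobe. It then assigns the right lung to the first bronchoscopy (Visit 3) and says that "at second bronchoscopy (Visit 8) samples will be taken from the left side". That assignment covers all samples.

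Three sets of outcomes draw on the biopsies:
- Secondary endpoint 1 in section 7.1: "Change in cellular populations and gene expression of T2-related signalling pathways in bronchial biopsies pre- and post benralizumab".
- Secondary endpoint 3 in section 7.1, which is the same kind of change for remodelling pathways.
- The primary outcome as worded in section 10.3, which covers "samples derived from bronchoscopy including bronchial biopsies, bronchoalveolar lavage (BAL) and bronchial brushings". The primary endpoint in section 7.1 is limited to BAL.

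Section 14.2 states that "All analyses will be paired, considering patient-specific changes". There is no control group. The Retention paragraph of section 8 says that "a standardised sedation and periprocedural protocol will be used to maintain consistency in sampling and patient experience", but gives no rule on lobes.

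**The concern.** The right lung has an upper, a middle and a lower lobe; the left has only an upper and a lower. An operator at Visit 8 therefore cannot carry out the whole biopsy instruction. The choice is to take everything from the lower lobe or to substitute some part of the upper lobe, and the protocol does not say which. If Visit 3 is done as written, the pre-treatment set includes tissue from a lobe that the post-treatment set cannot include.

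A paired analysis removes what is stable within a patient. It does not remove a difference in sampling site that runs the same way in every patient. With no control group, nothing else in the design separates a lobe difference in cell density, wall structure or gene expression from an effect of benralizumab. For the spatial work, position and cell-to-cell interaction within the biopsy are themselves outcomes (section 14.2). A mismatch cannot be repaired once the Visit 3 biopsies have been taken.

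**Working it through.** The protocol gives no figure on this point to reproduce. The core of the check sets the statements side by side.

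1. Required lobes: lower and middle, with no exception by visit (section 10.3).
2. Side: right at Visit 3, left at Visit 8, for all samples (section 10.3).
3. Lobes available: right lung upper, middle and lower; left lung upper and lower. This is basic anatomy and is not stated in the protocol.
4. At Visit 3 the required lobes both exist, so the rule can be met in full. At Visit 8 only the lower lobe exists, so the rule can be met in part.
5. Sections 6, 7, 9.3, 10.3, 13.1 and 14.2 contain no mention of the lingula or another left-sided counterpart, and no text confines the middle-lobe instruction to Visit 3.
6. The text does not say which biopsies are analysed. Section 6 (secondary objective 1) plans two sequential cryosections from each patient's biopsies before and after treatment, without saying which of the up to 6 biopsies they come from.

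**Size, as an illustration only.** Suppose a share *m* of the analysed Visit 3 biopsies is middle-lobe and all analysed Visit 8 biopsies are lower-lobe. Let *d* be the middle–lower difference in units of the SD of the paired change. The false shift is then

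δ = *m* × *d*.

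Neither *m* nor *d* is in the documents. I assume *m* = 0.50 and *d* from 0.1 to 0.5.

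For a paired t-test with n = 12 (the planned number of subjects), two-sided 5%, the critical value on 11 degrees of freedom is 2.201. The non-centrality parameter is δ√12. The rejection rate when treatment has no effect is the probability that a non-central t on 11 degrees of freedom falls outside ±2.201.

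| *d* (assumed) | δ = 0.50 × *d* | δ√12 | Rejection rate under no treatment effect |
|---|---|---|---|
| 0 | 0 | 0 | 5.0% |
| 0.1 | 0.05 | 0.173 | 5.3% |
| 0.2 | 0.10 | 0.346 | 6.2% |
| 0.5 | 0.25 | 0.866 | 12.4% |

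At the low end the effect is negligible; at the high end the error rate is about two and a half times nominal (12.4 / 5 = 2.5). Nothing in the documents says where in this range, or outside it, the truth lies.

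**The case against.** The strongest case on the other side is that this is a wording gap in one sentence, affecting endpoints that section 7.1 classes as secondary, in a 12-patient mechanistic study without a power calculation. An experienced operator may use the lingula as the left-sided equivalent by habit. The CRF already holds a record of bronchoscopy procedures (sections 10.5 and 13.2), and section 10.2 promises sample-specific SOPs. Much of this is fair, but it leaves the contradiction standing. The lingula is not named and belongs to the upper lobe, so the lobes would still differ. Neither the CRF description nor section 10.2 mentions biopsy site.

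A reader might infer more than the text supports, in four ways.

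- *That the analysed samples must differ in lobe in all 12 patients.* They need not. Lower-lobe tissue is available at both visits, and the analysed pairs could be matched on lobe. The protocol permits a mismatch and does not guard against it, but does not force one.
- *That the bias is independent of the right-then-left order.* The unworkable wording is independent of it; the bias is not. If side order were balanced across patients, the lobe shift would reverse in half of them and the average bias would largely cancel, leaving added variance. The bias keeps one direction because the order is fixed.
- *That the rejection rates above are the study's error rates.* They rest on assumed inputs and a single uncorrected t-test. Section 14.2 plans dedicated pipelines and multiple-test correction for the transcriptomic data.
- *That BAL and brushings share the fault.* No lobe is named for either, so the contradiction concerns biopsies only.

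**Conclusion.** The two sentences in section 10.3 cannot both be met in full at Visit 8. This is a stated rule that fails, not a detail that could be left to a statistical analysis plan. Under the fixed side order, the pre-treatment biopsies may include middle-lobe tissue that the post-treatment biopsies cannot. Any lobe difference would then be read as treatment change in secondary endpoints 1 and 3 of section 7.1, and in the primary outcome as section 10.3 words it.

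The contradiction is certain, but its effect on the results is unknown, because the documents give neither the split by lobe nor the variation between lobes. The range of 5.3% to 12.4% holds only for a false shift of 0.05 to 0.25 SD, 12 complete pairs and one paired t-test at 5%. It shows that the consequence could be anything from trivial to material, and does not measure it. The reason to act is that correction is cheap now and impossible after sampling.

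**What to change.** In section 10.3, reconcile the biopsy sentence with the side assignment so that every named site exists in both lungs, or state the left-sided counterpart explicitly. Which sites to use is for the investigators to decide and none is proposed here. Add that the biopsies used for spatial transcriptomics and histology must come from corresponding sites at Visits 3 and 8. Add a CRF field for the site of each biopsy, so that the match can be verified and any departure reported.

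The cost is a sentence or two and one CRF field. The small downside is less freedom in choosing sites when a segment is awkward to biopsy. The change does not remove the wider limit that all pre-treatment samples come from the right lung and all post-treatment samples from the left; that confounding of side with time point remains.

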10.4 Sample Storage Procedures

Samples will be appropriately stored in temperature controlled fridge, freezers and liquid nitrogen dewars which are remotely monitored 24hr. These temperature records will be filed for laboratory audit purposes to ensure and to show that the integrity of the stored samples have not been compromised. Inventory logs of all study samples will be maintained and storage positions in the freezers and dewar will be clearly recorded.

The samples will be stored in secure freezers in laboratories within the School of Immunology and Microbial Sciences at King's College London and GSTT sites linked to the direct care team.

Overall custodial arrangements will be with the Chief Investigator and access will only be provided to the study team or delegates of the study team (as decided by the chief Investigator).

The HTA site license number is 12521 for the KCL Guy's campus site. The designated individual is [name].

10.5 Data Recording/Reporting

Enrolment into the study will be documented in each participant's medical notes. Data collection will comprise of a paper case report form (CRF) including participant demographics, asthma characteristics (e.g. age of onset, atopic status, T2 biomarker levels, presence of nasal polyposis etc), pulmonary function test results and record of bronchoscopy procedures.

All data will be handled within the conditions of the General Data Protection Regulations (GDPR) which came into force in May 2018 with the participant's informed consent form. Confidential information, both medical records and personal information will only be accessible by members of the GSTT direct care team. Recruited participants will be pseudonymised (given a code) and any data

records will be referred to by this code. Data will be archived according to current ICH GCP guidelines. Laboratory books containing results of the study will not contain personal information.

A combination of paper and electronic records will be used. The paper records will be filed in the study-specific folder and will also be scanned and filed electronically on KCL and GSTT servers on computers that are password protected.

Molecular data:

Sequencing datasets: sequencing datasets will be stored in local servers at King's College London (KCL) and in double-password protected hard drives which will be kept in a locked cabinet. Integration of the transcriptomics and clinical datasets will be done in local machines at KCL; if more computational power is required we will leverage on the cloud resources such as our local high Performance Computer (Rosalind) or Cyverse. Patient datasets will be pseudonymised and all data handling in the cloud will be done in accordance with GDPR regulations.

Strict measures will be in place to safeguard the confidentiality of all data collected. All laboratory specimens and forms, laboratory reports, study data collection tools and stored samples will be identified using unique study numbers alone, to maintain participant confidentiality. No personal identifier information will be shared or recorded on any of these forms or samples and their associated databases. Personal identifiers (e.g. name and contact details) will only be collected for (1) informed consent and (2) logistical purposes. Personal identifiers will appear on consent forms and paper enrolment logs only. These will NOT include any sensitive study information. The unique study number will link personal identifiers to study information. All electronic data will be stored in a password protected database systems on password protected computers, servers and networks. No individuals will ever be identified when reporting study findings or making sequencing data publicly available at the time of publication.

10.6 Sample Receipt/Chain of Custody/Accountability

Firstly, a materials transfer agreement will be in place between the GSTT and KCL site for sample transfer and chain of custody processes. Laboratory SOPs are in place to meet GCLP and HTA compliance. Sample receipt and processing worksheets will be in place for each sample type to record the patient code number, visit number, date, time and condition of the samples upon arrival to the laboratory. Sample labelling will be maintained throughout the processing and storing procedure.

10.7 Sample Transfer to sites outside the Organisation

Where study samples will need to be transferred outside the organisation to fulfil the endpoints of the study. These will be appropriately packed and sent with a medical courier with documentation of sample code, sample type, volume and safety guidelines and transported at an appropriate temperature.

In the study, biological samples [blood, lung biopsies and lavage fluid and airway cells] will be collected from patients in accordance with the patient consent form and patient information sheet and shall include all tissue samples or other biological materials and any derivatives, portions,

progeny or improvements as well as all patient information and documentation supplied in relation to them. Further, the custodian of the Materials will use the Materials for the Study only. For the avoidance of doubt Recipient shall only use the Material in accordance with the consent provided by the Study Donors (if applicable) and shall always use the Materials with dignity and respect and shall always use good laboratory practice in handling Materials

The chief investigator and study co-investigator [[name] at King's College London] will process, store and dispose of the study samples [blood, lung biopsies and lavage fluid and airway cells] in accordance with all applicable legal and regulatory requirements, including the Human Tissue Act 2004 and any amendments thereto. While Provider uses reasonable endeavours to ensure the quality of the Materials, the Materials are provided 'as is' and it makes no representation and gives no warranty or undertaking in relation to the Materials, including but not limited to its safety, fitness for purpose or use of any kind.

After ethics approval for the study has expired, the study samples [blood, lung biopsies and lavage fluid and airway cells] will be disposed of in accordance with the Human Tissue Act 2004, and any amendments thereto, or transferred to a licensed tissue bank.

11 Assessment of Safety

An Adverse event (AE) is the development of an undesirable medical condition or the deterioration of a pre-existing medical condition following or during exposure to a pharmaceutical product, whether or not considered causally related to the product. An undesirable medical condition can be symptoms (e.g. nausea, chest pain), signs (e.g. tachycardia, enlarged liver) or the abnormal results of an investigation (e.g. laboratory findings, electrocardiogram). In clinical studies, an AE can include an undesirable medical condition occurring at any time, including run-in or washout periods, even if no study treatment has been administered. The term AE is used to include both serious and non-serious AEs.

An SAE is an AE occurring during any study phase (i.e., run-in, treatment, washout, follow- up), that fulfils one or more of the following criteria:

- Results in death
- Is immediately life-threatening
- Requires in-patient hospitalization or prolongation of existing hospitalization
- Results in persistent or significant disability/incapacity or substantial disruption of the ability to conduct normal life functions
- Is a congenital anomaly or birth defect
- Is an important medical event that may jeopardize the subject or may require medical intervention to prevent one of the outcomes listed above

An adverse drug reaction is the development of an undesirable medical condition or the deterioration of a pre-existing medical condition following or during exposure to a medicinal product, suspected to be causally related to the product.

Participants will be asked about the occurrence of any AEs at each visit and will be asked to report AEs to the study direct care team between visits. AEs will be assessed by the CI/PI for causality, intensity, seriousness and expectedness. All AEs will be recorded in the CRF and reported to the Sponsor as per their guidelines. Any adverse events that do occur and are considered by the PI to be related to the investigations will be expedited to the Sponsor and REC within 7 days. Lists of the AEs will be provided to the Sponsor when requested.

All SAEs will be recorded on a Serious Adverse Event Form and will be reported within 24 hours of awareness to the Sponsor. All SAEs occurring to a research participant that the CI feels was related i.e. resulted from administration of any of the research procedures, and unexpected i.e. the type of event not listed in the protocol as an expected occurrence will be reported to the appropriate REC.

